### 4.3.5 Vital Signs, Physical Examination Findings, and ECG

#### 4.3.5.1 Vital Signs

Descriptive statistics for vital signs parameters and changes from baseline will be presented by visit and treatment group. Orthostatic hypotension will be defined as either

- (Supine systolic BP – standing systolic BP)  $> 20$  mmHg
- (Supine diastolic BP – standing diastolic BP)  $> 10$  mmHg

A listing will be presented at each time point for all participants in the safety analysis set.

#### 4.3.5.2 Physical Examinations

Physical examination findings, including neurological examination findings, will be listed for all participants in the safety analysis set as “Normal”, “Abnormal-Clinically Significant”, and “Abnormal-Non-Clinically Significant”. Clinically significant findings will be included as TEAEs.

#### 4.3.5.3 ECG

Descriptive statistics for ECG parameters will be listed and summarized by treatment group.

ECG interpretation will be categorized as normal; abnormal, not clinically significant; and abnormal, clinically significant. Clinically significant findings for ECG will be recorded as TEAEs, listed, and tabulated.

### 4.3.6 Other Safety Analyses

Positive pregnancy tests will be presented in a listing.

Ophthalmic exam and C-SSRS findings will be listed.

## 4.4 OTHER EXPLORATORY ANALYSIS

A subgroup analysis of the proportion of participants who discontinue treatment up to Week 12 will be made to assess consistency of the intervention effect across the subgroups:

- Above and below median UPDRS part III at baseline
- Age group:  $< 65$  vs  $\geq 65$  years
- Sex: female vs male
- Baseline CSBM  $\leq 3$  vs CSBM  $> 3$

If the number of participants is too small (less than 10%) within a subgroup, then the subgroup categories may be redefined prior to unblinding the study.

## 5 INTERIM ANALYSIS AND DATA MONITORING COMMITTEE

### 5.1 INTERIM ANALYSIS

An interim analysis will not be conducted. Final analysis will be performed at the end of the 12-week placebo-controlled study and will include all safety and efficacy endpoints. The study team will be unblinded for the Final analysis.

### 5.2 DATA SAFETY MONITORING BOARD

A Data Safety Monitoring Board (DSMB) will meet on a regular basis to review safety data, as outlined in the DSMB charter. The DSMB will consist of at least two expert clinicians who are actively treating PD participants, and a biostatistician.

## 6 SUMMARY OF MAJOR CHANGES IN THE PLANNED ANALYSES

The definition of mITT was changed to exclude those who were randomized prior to Protocol version 6.1. A Full Analysis Set (FAS) was defined to include everyone who meets the other requirements for inclusion in the mITT, including those randomized prior to Protocol version 6.1. The FAS will be used to perform a sensitivity analysis on the MDS-UPDRS Parts II+III.

The order of hierarchical testing for statistical significance was changed to test all endpoints in the highest dose first (200 mg), then the 100 mg dose, then the 50 mg dose. Testing order of the endpoints was changed.

## 8 APPENDICES

### 8.1 PARTIAL DATES FOR ADVERSE EVENTS AND PRIOR/CONCOMITANT MEDICATION

Dates missing the day or both the day and month of the year will adhere to the following conventions in order to classify treatment-emergent AEs and to classify prior/concomitant medications:

#### Adverse Events

- The missing day of onset of an AE will be set to:
  - First day of the month that the event occurred, if the onset YYYY-MM is after the YYYY-MM of first study treatment

- The day of the first study treatment, if the onset YYYY-MM is the same as YYYY-MM of the first study treatment
  - The date of informed consent, if the onset YYYY-MM is before the YYYY-MM of the first treatment.
- The missing day of resolution of an AE will be set to:
  - The last day of the month of the occurrence. If the participant died in the same month, then set the imputed date as the death date.
- If the onset date of an AE is missing both the day and month, the onset date will be set to:
  - January 1 of the year of onset, if the onset year is after the year of the first study treatment
  - The date of the first treatment, if the onset year is the same as the year of the first study treatment
  - The date of informed consent, if the onset year is before the year of the first treatment
- If the resolution date of an AE or end date of an IP is missing both the day and month, the date will be set to:
  - December 31 of the year of occurrence. If the participant died in the same year, then set the imputed date as the death date.

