9.3.1. Time Period and Frequency for Collecting AE and SAE Information

All SAEs will be collected from the signing of the ICF until the follow-up visit at the timepoints specified in the SoA (Section 1.3).

All AEs will be collected from the signing of the ICF until the follow-up visit at the timepoints specified in the SoA (Section 1.3).

During the screening period baseline abnormalities (any sign or symptom present, such as abnormal screening laboratory value) will be assessed for clinical significance and captured in medical history as ongoing. Any baseline abnormality that increases in severity or frequency should be captured as an adverse event if determined clinically significant by the investigator. All SAEs will be recorded and reported to the sponsor or designee immediately and under no circumstance should this exceed 24 hours, as indicated in Appendix 3. The investigator will submit any updated SAE data to the sponsor within 24 hours of it being available.

Investigators are not obligated to actively seek information on AEs or SAEs after conclusion of the study participation. However, if the investigator learns of any SAE, including a death, at any time after a participant has been discharged from the study, and he/she considers the event to be reasonably related to the study intervention or study participation, the investigator must promptly notify the sponsor.

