#### **3.4.2 Adverse events**

The adverse event verbatim descriptions (investigator terms from the CRF) will be classified into medical terminology using the Medical Dictionary for Regulatory Activities (MedDRA). Adverse events will be coded to primary System Organ Class (SOC) and preferred term (PT) using MedDRA, Version 26.0 or newer.

A treatment-emergent adverse event (TEAE) is defined as an AE that had an onset date, or a worsening in severity from baseline (pre-treatment), on or after the first dose of study intervention up to the Safety follow-up visit or Early Termination Visit following study drug discontinuation.

An AE will be considered treatment related if the investigator considers that there is a reasonable possibility that the event may have been caused by the investigation product. If a causal relationship to study intervention is missing for an AE that started on or after the date of first dose of study intervention, causality will not be imputed and a category of “missing” will be included as necessary in incidence summaries. An event with missing onset date will be imputed as treatment-emergent, unless there is other evidence that confirms that the event was not treatment-emergent (e.g., the event end date was prior to the study intervention start date).

---

An AE will be considered serious (SAE) if it meets the definition of SAE given in the protocol Appendix 10.3.2, as recorded on the AE form of the CRF.

If AE have missing or incomplete start or end dates, they will be imputed as described in [Appendix 8.1](#).

The SOCs will be presented in alphabetical order and the PTs will be presented in frequency order for the highest dose of active treatment within each SOC. A participant who reports more than 1 AE in different SOCs will be counted once in the overall total. A participant who reports AEs in different PTs in the same SOC will be counted only once in the SOC total. A participant reporting more than 1 AE in a given PT will be counted only once for that term. In severity and relatedness tables, the most severe or related AE will be counted.

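### SAP Appendix 8.1 imputes partial AE onset dates to the day of first dose without checking the recorded end date, so a screening event that ended before dosing can be counted as treatment-emergent.

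*SAP*

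**What the plan says.** SAP Appendix 8.1 gives its partial-date conventions "in order to classify treatment-emergent AEs and to classify prior/concomitant medications", so the imputed date feeds the TEAE flag. Where only the onset day is missing, the onset becomes "The day of the first study treatment, if the onset YYYY-MM is the same as YYYY-MM of the first study treatment". Where day and month are both missing, it becomes "The date of the first treatment, if the onset year is the same as the year of the first study treatment". Neither bullet refers to the end date.

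SAP 3.4.2 defines a TEAE by onset, or worsening in severity, on or after first dose. It adds a default: "An event with missing onset date will be imputed as treatment-emergent", "unless there is other evidence that confirms that the event was not treatment-emergent". The example it gives of such evidence is "e.g., the event end date was prior to the study intervention start date". Later in the section, a sentence beginning "If AE have missing or incomplete start or end dates" sends those dates to Appendix 8.1.

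Protocol 9.3.1 states that "All AEs will be collected from the signing of the ICF until the follow-up visit". Protocol 4.1 allows up to 28 days of screening. Adverse events with onset and resolution before Day 1 can therefore be in the database.

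**The concern.** TEAE incidence is a primary safety endpoint (SAP 1.2.1). An event that ended before the participant took any study drug does not belong in it. The Appendix 8.1 onset rules can nevertheless put such an event on the day of first dose, where it meets the TEAE definition and would enter the incidence, severity and relatedness tables.

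The two SAP sections may also treat near-identical records differently. With no onset information at all, 3.4.2 uses the end date and excludes the event. With the onset month known, Appendix 8.1 followed literally includes it. Knowing more then gives the worse answer, and two programmers could reasonably produce different TEAE counts from the same data.

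**Working it through.** The plan states no figure on this point, so the check is of date logic.

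**Worked example** (illustrative dates). First dose is 2024-07-20.

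| Recorded onset | Recorded end | Rule applied | Imputed onset | TEAE? |
|---|---|---|---|---|
| 2024-07 (day missing) | 2024-07-08 | Appendix 8.1 alone | 2024-07-20, 12 days after the end | Yes |
| 2024-07 (day missing) | 2024-07-08 | Appendix 8.1 date, with the 3.4.2 exception read to cover partial onsets | 2024-07-20, 12 days after the end | No |
| Wholly missing | 2024-07-08 | 3.4.2 default and exception | None; Appendix 8.1 has no AE rule for this | No |
| 2024 (day and month missing) | 2024-06-30 | Appendix 8.1 alone | 2024-07-20, 20 days after the end | Yes |

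**All cases in one month.** Take a 31-day month with the onset day unknown, and every pairing of first-dose day and complete end day.

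- Pairs: 31 × 31 = 961.
- Pairs with the end before first dose: 0 + 1 + … + 30 = 31 × 30 / 2 = 465.
- Appendix 8.1 alone: 465 of 465 get an onset after their end, and 465 of 465 are flagged TEAE.
- With the 3.4.2 exception extended to partial onsets: 0 of 465 are flagged, but 465 of 465 still carry an onset after their end.
- With the imputed onset also capped at the end date: 0 flagged and 0 inverted.

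**Can the situation arise?** Assume a full 28-day screening period and first-dose dates spread evenly over a 366-day year. A dose on day d of a month has min(d − 1, 28) of the preceding 28 days in the same month. Summed over dose days, that is 462 for a 31-day month, 434 for a 30-day month and 406 for a 29-day month. The share is (7 × 462 + 4 × 434 + 406) / (366 × 28) = 5,376 / 10,248, or about 52%. So about half of screening days share a calendar month with first dose. This shows only that the overlap is common; it does not count affected events.

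**Effect per participant.** SAP 1.3.1 reports 11 + 126 = 137 enrolled. Assuming equal arms, 137 / 4 is about 34, and 1 / 34 is about 3 percentage points. This applies only to a participant with no other TEAE in the table row concerned.

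**The case against.** The strongest reply is that SAP 3.4.2 already names this case: an end date before the start of study drug is its own example of evidence against treatment emergence. If that exception also governs partial onsets, none of the 465 cases is flagged. A reader might infer that the plan definitely counts resolved screening events as TEAEs, and the documents do not support going that far.

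The narrow reading is still the more natural one. The exception speaks of a missing onset date, while the same section separately refers missing or incomplete dates to Appendix 8.1. Appendix 8.1 has no rule for a wholly absent AE onset, which is exactly the gap that the 3.4.2 sentence fills. Even the broad reading leaves imputed onsets later than recorded ends. The SAP guards against a similar problem for medications: with a null start date and a complete end date not after the first study visit, the start is set to the end date. The AE rules have no counterpart.

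A reader might also infer that these events would be listed as Day 1 onsets. SAP 2.3.2 contradicts that, since Study Day for partial dates appears as partial or missing in listings.

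Three mitigating points stand. Protocol 9.3.1 sends baseline abnormalities found at screening to medical history, which reduces the number of pre-dose AEs. Safety is summarized descriptively, with no inferential test (SAP 4.3.2). Events that ended before dosing cannot be caused by the assigned drug, so there is no reason to expect the misclassification to favor one arm systematically.

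**Conclusion.** The point holds as a minor defect. Appendix 8.1 lacks an end-date check and is not aligned with 3.4.2. Followed literally, it gives an onset after the event's own end and can turn a resolved screening event into a TEAE. Whether it does so depends on how the programmer reads the 3.4.2 exception; the inverted dates remain on either reading.

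The number of events with an incomplete onset and an end date known to precede first dose is not in the documents and is probably small. The effect of about 3 percentage points per affected participant rests on roughly equal arms of about 34 and on that participant having no other TEAE in the row. The documents do not support inferring a bias between arms or any effect on the efficacy analyses.

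**What to change.** In Appendix 8.1, add to both the missing-day and the missing-day-and-month AE onset rules:

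- The Section 3.4.2 exception also applies to partial onset dates: an AE whose recorded end date is before first dose is not treatment-emergent.
- An imputed onset may not be later than the recorded end date and must stay within the recorded onset month or year. For an event that ended before first dose, use for example the later of the informed consent date and the first day of that period.

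The second condition avoids a new error. Suppose consent was on 2024-06-25 in the example above. Setting the onset to the consent date alone would give a June onset for an event recorded as starting in July. The later of 2024-06-25 and 2024-07-01 is 2024-07-01, which respects both the recorded month and the end date of 2024-07-08.

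The cost is a sentence or two in the SAP and matching conditions in the AE derivation. No new data are needed.

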### **Prior/concomitant medication**

- The missing day of start date of a therapy will be set to the first day of the month that the event occurred.
- The missing day of end date of a therapy will be set to the last day of the month of the occurrence.
- If the start date of a therapy is missing both the day and month, the onset date will be set to January 1 of the year of onset.
- If the end date of a therapy is missing both the day and month, the date will be set to December 31 of the year of occurrence.
- If the start date of a therapy is null and the end date is not a complete date then the start date will be set to the earlier of the imputed partial end date and the date of the first study visit.

- If the start date of a therapy is null and the end date is a complete date
  - and the end date is after the date of the first study visit then the start date will be set to the date of the first study visit.
  - otherwise the start date will be set to the end date of the therapy.
- If the end date of a therapy is null and the start date is not a complete date then the end date will be set to the study end date.
- If the end date of a therapy is null and the start date is a complete date
  - and the start date is prior to the study end date then the end date will be set to the study end date.
  - otherwise, the end date will be set to the start date of the therapy.

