6.2. Exclusion Criteria

Participants are excluded from the study if any of the following criteria apply:

Medical Conditions

1. Diagnosis/suspicion of secondary or atypical parkinsonism
2. Previous procedure or surgery for PD, or anticipation of these during the study
3. High likelihood of needing anti-parkinsonian treatment over the study period, in the opinion of the investigator
4. Clinically significant orthostatic hypotension
5. Clinically significant hallucinations requiring antipsychotic use in the 12 months prior to Screening
6. Clinically significant medical, surgical, psychiatric, or laboratory abnormalities in the judgement of the treating investigator or the EAC

Prior/Concomitant Therapy

1. Past treatment with levodopa, dopaminergic agonists, monoamine oxidase-B inhibitors, supplements containing levodopa (i.e. *Mucuna pruriens*) or A2A antagonists for more than 28 days, or treatment with any of these medications or supplements within 28 days prior to screening
2. Past treatment with irreversible monoamine oxidase-B inhibitors (e.g., selegiline) for more than 28 days; must be discontinued for at least 90 days before screening
3. Currently receiving moderate or strong Cytochrome P450 (CYP) 3A4/5 inducers or CYP3A4/5 inhibitors (except for topical administration)

4. Currently receiving any antipsychotic, metoclopramide, reserpine, or amphetamine.

Prior/Concurrent Clinical Study Experience

1. Current participation in another investigational clinical trial and/or receipt of any investigational medication within 90 days prior to screening
2. Previous randomization into this or another IkT-148009 study

Diagnostic Assessments

1. Active suicidal ideation within one year prior to screening visit, as determined by the Columbia Suicide Rating Scale (answer of “yes” on question 4 or 5)
2. Current diagnosis or history of substance abuse (excluding nicotine or caffeine) by Diagnostic and Statistical Manual of Mental Disorders (DSM)-5 criteria
3. Medical or recreational use of marijuana in the 3 months prior to the screening visit
4. Any social or behavioral reason that would preclude completion of the study, in the judgement of the investigator
5. Any skin condition that would interfere with obtaining adequate samples

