#### 4.1.5 Prior and Concomitant Therapy

All investigator terms for medications recorded on the CRF will be coded using the World Health Organization (WHO) Drug Dictionary Enhanced, March 2018 or newer. The number and percentage of participants who took prior and concomitant medications will be summarized for the Safety population by treatment, Anatomical Therapeutic Chemical (ATC) Classification and WHO Drug preferred term. Prior medications will be defined as medications that stopped prior to the first dose of study drug. Concomitant medications will be defined as medications that (1) with a start date before the first dose of study drug and an end date after the first dose of study drug or ongoing, or (2) with a start date on or after the date of the first dose of study drug up to 14 days following the last dose.

Common PD therapies are listed in Table 4-2. All ATC2 codes of ‘N04’ will be included as anti-Parkinson medication.

Table 4-2 Common PD therapies.

Drug class	Medication
Levodopa	Carbidopa-levodopa Levodopa Duodopa
Dopamine agonists	Pramipexole Rotigotine Apomorphine Ropinirole Stalevo
MAO B inhibitors	Selegiline Rasagiline Safinamide
COMT inhibitors	Entacapone Opicapone Tolcapone
Anticholinergics	Benzatropine Trihexyphenidyl
Mixed mechanism	Amantadine
Adenosine A2A receptor antagonist	Istradefylline

COMT= Catechol-O-methyltransferase; MAO= monoamine oxidase.

Summary tables will be provided for prior PD therapies and prior and concomitant general medications along with supportive listings. Listings will include indication, start date, stop date (or ongoing), and dosage information.

Medications known to be Cytochrome P450 (CYP) 3 A4/5 inhibitors or inducers and those known to be MDR1 or BCRP inhibitors will be listed separately and marked as prior or concomitant (see <https://www.fda.gov/drugs/drug-interactions-labeling/drug-development-and-drug-interactions-table-substrates-inhibitors-and-inducers> for the list of drugs in this category).

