#### 4.2.5 Sensitivity Analyses

As a sensitivity analysis for the MDS-UPDRS Parts II + III, the MMRM will be repeated as described in [Section 4.2.3](#) using the FAS.

Any efficacy endpoints that reach statistical significance may also be further explored on a post hoc basis using sensitivity analysis in which the Hypothetical Scenario is applied to Intercurrent Events, using the assumptions of Missing at Random (MAR) and Missing Not at Random (MNAR), respectively, to perform Multiple Imputation (MI) to impute data after the first occurrence of PD medication use. For MI using MNAR, copy-reference (placebo) will be used.

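### SAP Appendix 8.1 pushes year-only and blank medication end dates past first dose even when the drug is known to have stopped, so some past PD drugs are counted as concomitant

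*SAP*

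**What the plan says.** **End dates.** SAP Appendix 8.1 (Prior/concomitant medication) has three extension rules:
- Day missing: "The missing day of end date of a therapy will be set to the last day of the month of the occurrence".
- Day and month missing: if the "end date of a therapy is missing both the day and month, the date will be set to December 31" of that year.
- End date blank: the study end date, unless a complete start date is not before study end.

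None of them mentions first dose, an ongoing field, or evidence of stopping. The opening of Appendix 8.1 says the conventions serve to classify treatment-emergent AEs and prior or concomitant medication.

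**Classification.** SAP 4.1.5: "Prior medications will be defined as medications that stopped prior to the first dose of study drug". A drug started before first dose is concomitant if it ended after first dose or is ongoing. The same section plans a summary table of prior PD therapies and tables of prior and concomitant general medications.

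**Eligibility.** Protocol 6.1 requires that participants receive no anti-parkinsonian therapy. Protocol 6.2 excludes more than 28 days of past levodopa, dopaminergic agonists, MAO-B inhibitors or A2A antagonists, "or treatment with any of these medications or supplements within 28 days prior to screening". A short past course with an earlier stop is therefore allowed.

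**Adverse events, for comparison.** For an AE with a missing onset date, SAP 3.4.2 presumes treatment emergence "unless there is other evidence that confirms that the event was not treatment-emergent". Medications have no matching clause.

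**The concern.** Extending an unknown end date is a cautious default when nobody knows whether the drug was still being taken. It gives a wrong answer when stopping before first dose is already established. For the washout-listed PD drugs, eligibility itself establishes it. Short past courses are permitted, so such records can be expected in this trial.

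The prior PD therapies table is where the report of an untreated-PD trial shows how untreated the participants were. The rule can remove real past use from that table and add PD-drug use on study that did not happen. SAP 2.2 also identifies protocol deviations partly by program, so a false concomitant PD drug could raise a flag that then has to be cleared by hand.

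**Working it through.** The plan states no figure for this, so there is none to reproduce. The check applies the Appendix 8.1 rules to calendar dates and classifies the results by SAP 4.1.5.

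**Inputs.** L is the number of days from the true stop to first dose. Screening runs from Day -28 to Day -1 (Protocol 1.3) and the washout is 28 days before screening, so L is about 29 or more for the washout-listed drugs. Assumption, not from the documents: first-dose dates are spread evenly over a 365-day year.

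**Year-only end date.** The stop falls in the first-dose year when first dose is later than day L of the year, which is 365 − L of the 365 days. The imputed 31 December is strictly after first dose on one day fewer, because first dose on 31 December itself gives equality.

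| L (days) | Same year: (365 − L)/365 | Imputed end strictly after first dose: (364 − L)/365 |
|---|---|---|
| 29 | 336/365 = 92.1% | 335/365 = 91.8% |
| 90 | 275/365 = 75.3% | 274/365 = 75.1% |
| 180 | 185/365 = 50.7% | 184/365 = 50.4% |
| 270 | 95/365 = 26.0% | 94/365 = 25.8% |
| 365 or more | 0% | 0% |

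Example: first dose is 15 March 2024 and the drug stopped in January 2024. Recorded as 2024, the end becomes 31 December 2024 and the drug is concomitant. Had the stop been in 2023 and recorded as 2023, the end would be 31 December 2023 and the drug would stay prior.

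**Day-missing end date, washout-listed drugs.** At L = 29 the month end is strictly after first dose only if the stop was on the 1st of a 31-day month (first dose on the 30th, month end on the 31st). There are seven such months: 7/365 = 1.9%. From L = 30 the count is 0.

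**Day-missing end date, other drugs.** CYP3A4/5 inhibitors and inducers are excluded only if current. Amantadine, anticholinergics and COMT inhibitors are in SAP Table 4-2 but not in the 28-day washout list, so shorter lags are possible. Stop and first dose share a month on 365 − 12L days (for L up to 28):
- L = 7: 281/365 = 77%; strictly after first dose, (281 − 12)/365 = 74%.
- L = 14: 197/365 = 54%; strictly after first dose, (197 − 12)/365 = 51%.

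**Blank end date.** With a start before first dose, the end becomes the study end date and the drug is always concomitant. That is correct if it is ongoing and wrong if it had stopped.

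**Start dates.** A partial start goes to the first of the month or 1 January, without the floor that the AE rule has ("The date of the first treatment, if the onset year is the same as the year of the first study treatment"). A drug begun on study and dated too early still ends after first dose or is ongoing, so it stays concomitant. Only its apparent start moves.

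**The case against.** The strongest defence is that latest-end imputation is deliberately conservative. It avoids missing true concomitant use, and a year-only stop in the first-dose year may belong to a drug that did continue past first dose. SAP 4.1.5 lists a stop date or ongoing status, so a blank stop may simply mean ongoing. All of this stands. It supports keeping the rule where stopping is unknown, but not applying it where stopping is recorded.

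A reader might infer more than the documents support:
- *That past PD drugs are generally reclassified.* They are not. A stop in an earlier year stays prior, and the month-end rule almost never touches washout-listed drugs.
- *That the efficacy result is biased.* The SAP 4.2.3 MMRM follows treatment policy and uses no medication dates. Only SAP 4.2.5 could use them, through its plan to "impute data after the first occurrence of PD medication use". That analysis is optional, post hoc and limited to endpoints reaching significance, and nothing says Appendix 8.1 dates define that first occurrence.
- *That eligibility breaches would be falsely declared.* SAP 2.2 combines program checks with monitor reports and a review before lock. It does not say that imputed dates feed the checks, and the Enrollment Authorization Committee confirms eligibility separately.
- *That on-study PD drugs would often carry year-only start dates.* Protocol 7.6 requires dates and asks about medication at every visit and call, and Protocol 7.6.1 involves the medical monitor when PD medication is started.

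**Conclusion.** The point holds within limits. When a drug is known to have stopped before first dose, Appendix 8.1 and SAP 4.1.5 together misclassify it if its end date is year-only in the first-dose year, or blank and not marked ongoing. For drugs outside the washout list, a day-missing stop in the month of first dose can do the same.

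The rates of 92%, 75% and 51% at 29, 90 and 180 days are conditional on a year-only stop date and on evenly spread first doses. They are not rates among participants. The number of partial dates is not given, so the number of participants affected cannot be computed and may be small. The consequence is a wrong entry in planned descriptive tables and possibly an unnecessary deviation flag. It does not reach the main efficacy analysis.

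**What to change.** Add to Appendix 8.1:
1. If the record shows that the therapy ended before first dose, cap the imputed end date at the day before first dose. Such a record is a stop reported at the screening or Day 1 medication review, or no ongoing mark together with evidence of earlier stopping.
2. Otherwise keep the current late-end rule, capped at the participant's own last study date. SAP 2.3.3 defines end of study by the last participant's last visit, so the present term can run past an individual's participation.
3. Only if Appendix 8.1 dates are used to time the start of PD medication: for a drug first reported after Day 1, set a partial start no earlier than first dose, within the recorded month or year, and on or before any recorded stop. Using the day after the last contact without a report is not safe without those bounds. A drug recorded as started in January, not reported at a 5 February call and reported later would be dated 6 February.

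With rule 1, drugs known to have stopped before first dose are misclassified in 0% of cases at every lag, and ongoing drugs are unaffected. The cost is a few sentences and a small programming change, ideally before unblinding. No new data are needed, because medications are already reviewed at every visit and call. If the plan can no longer be changed, note the rule as a deviation in the clinical study report, as SAP Section 1 provides.
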